Investigational sites will access randomization allocation via a password-protected system that can only be accessed by those approved by the study sponsor.

All study staff and necessary hospital personnel will be instructed that subjects are not to be informed of their randomization assignments and appropriate measures should be taken to minimize the risk of premature unblinding.

The Investigator performing the catheterization lab procedures and his/her designated study staff will be blinded to a subject's randomization group up until the angiography is completed and inclusion/exclusion confirmed following the angiography. However, investigators performing study follow-up visits and the subject's referring/managing physicians will not be proactively informed of a subject's treatment assignment to minimize potential bias in the subject's care decisions. To minimize potential bias in the measurement of Office BP and ABPM, each investigational site will specify several designated "blinded" members of their study staff that will not be informed of the subject's group assignments and will be responsible for performing the office blood pressure measurements, conducting ABPM preparation and printing results upon a patient completing the ABPM. Prior to unblinding, the effectiveness of blinding will be assessed by asking blinded study staff which group they believe the subject was randomized to.

Subjects will be blinded during the renal angiogram by a combination of conscious sedation, sensory isolation (e.g., blindfold and music), and lack of familiarity with the procedural details and duration (i.e., subjects will not know the difference between the renal angiography procedure alone and the renal angiography and denervation procedure). Subjects will continue to be blinded by only interacting with blinded site personnel through the 6-month follow-up visit post-procedure. Blinding effectiveness will be assessed by asking the subject which group they believe they were randomized to. All subjects will be unblinded after the completion of their required 6-Month follow-up testing.

8. Determination of Sample Size

This study will be conducted as an adaptive Bayesian trial with an informative prior. A Bayesian power prior approach [3,4] in conjunction with a discount function will be used to incorporate the prior data. The discount function reduces the strength of the prior data if disagreements are observed with the prospective data.

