9.1.4. Crossover Procedures

Control subjects may crossover to receive renal denervation therapy after completing their 6 month follow-up visit. For the subjects who have already completed their 6-month visit at the time crossover procedures are available per protocol, the decision to crossover must take place at their next in-person visit (6, 12, 24 and 36-month follow-up or Unscheduled visit). All subjects will have 30 days from that visit to undergo the crossover procedure. Subjects that are more than 30 days from 6, 12, 24 or 36-month or unscheduled visit, must complete a crossover baseline visit prior to having the crossover renal denervation procedure. To crossover, the required baseline data must be collected, and the subject cannot meet any of the anatomical or eGFR exclusion criteria. Crossover subjects will undergo follow up visits at 1, 3, 6, 12, 24, and 36 months post-procedure. Subjects who do not meet required eligibility for crossover on the day of the procedure will undergo follow-up visits according to their original follow-up schedule. Crossover procedures will be offered once and will not be available at a later time if it was declined by the control subject during the allowed 30-day window.

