The safety endpoints will be adjudicated by the Clinical Events Committee (CEC). The following algorithm will be used to evaluate the safety event rates: The denominator will include all subjects who either had a CEC adjudicated event prior to the time of interest (180 days for 6 months events, for example), or had last contact date that is beyond the lower window of the follow up (166 days for 6 month events, for example). The numerator will include all subjects who had CEC adjudicated events up to the time of interest (180 days for 6 months events, for example).

The secondary safety endpoints, out to 6-months follow-up, will be compared between RDN and control groups using Fisher's exact test. Two-sided 95% confidence intervals of the difference between treatment groups will also be presented.

After 6-months follow-up, control subjects may crossover (undergo renal denervation), and secondary safety endpoints will be summarized by group (RDN, Crossovers, Non-Crossovers). RDN vs. Crossover vs. Non-Crossover groups will be compared out to 36 months post-procedure using chi-square tests for categorical data and ANOVA for continuous data.

The secondary safety analyses will be performed using the ITT population defined in section 9.1.3.1.

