9.9.7. Secondary Efficacy Objectives

The following additional secondary efficacy endpoints will be assessed:

- Change in SBP from baseline (SV2) as measured by 24-hour ABPM at 3, 6, 12, 24 and 36 months post-procedure.
- Change in office SBP from baseline (SV2) at 1, 3, 6, 12, 24 and 36 months post-procedure.
- Change in DBP from baseline (SV2) as measured by 24-hour ABPM at 3, 6, 12, 24 and 36 months post-procedure.
- Change in office DBP from baseline (SV2) at 1, 3, 6, 12, 24 and 36 months post-procedure.

- Incidence of achieving target office SBP (SBP <140 mmHg) at 1, 3, 6, 12, 24 and 36 months post-procedure.

RDN vs. control groups will be compared out to 6-months post randomization, prior to the crossover procedure. Statistical comparisons will be performed using the independent samples t-test for continuous endpoints and Fisher's exact test for categorical endpoints. In addition, two-sided 95% confidence intervals of the difference between RDN and control groups will be presented. Changes in blood pressure measurements from baseline to follow-up within each treatment group will be assessed using paired t-tests. Two-sided 95% confidence intervals of the mean change from baseline will be presented for each treatment group. analysis of covariance (ANCOVA) models, adjusting the treatment effect for the baseline BP measurements will also be applied to all continuous secondary endpoints.

RDN vs. crossover vs. non-crossover groups will be compared out to 36 months post-procedure using chi-square tests for categorical data and ANOVA for continuous data.

Changes in blood pressure measurements from baseline to follow-up within each group will be assessed using paired t-tests. Two-sided 95% confidence intervals of the mean change from baseline will also be presented for each group.

The secondary efficacy analyses will be presented for all the study populations defined in section 9.1.3.

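### The 6-month safety count in SAP 9.9.2 runs to day 180 by randomized arm with no cut at crossover, so a complication of an early crossover denervation could be scored as a sham-control event (minor)

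*SAP*

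**What the plan says.** Three rules in the SAP meet here.

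- **Counting rule (9.9.2).** "The numerator will include all subjects who had CEC adjudicated events up to the time of interest (180 days for 6 months events", given as an example. The denominator takes subjects with an adjudicated event before that time, and those who "had last contact date that is beyond the lower window of the follow up (166 days for 6 month events, for example". The population is ITT, which 9.1.3.1 defines by randomized treatment.
- **Comparison (9.9.2).** "The secondary safety endpoints, out to 6-months follow-up, will be compared between RDN and control groups using Fisher's exact test". For the period after 6-month follow-up, when controls may cross over, "secondary safety endpoints will be summarized by group (RDN, Crossovers, Non-Crossovers".
- **Crossover (9.1.4).** "Control subjects may crossover to receive renal denervation therapy after completing their 6 month follow-up visit". On timing: "All subjects will have 30 days from that visit to undergo the crossover procedure". Section 7 ties unblinding to the same milestone: "All subjects will be unblinded after the completion of their required 6-Month follow-up testing".

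The secondary efficacy section (9.9.7) adds a limit that 9.9.2 lacks: "RDN vs. control groups will be compared out to 6-months post randomization, prior to the crossover procedure". Section 9.9.8 carries the same limit.

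**The concern.** Crossover is triggered by a visit, but the safety count ends on a fixed day. If the visit falls early in its window, the two overlap. A control denervated in the overlap is still a control in an as-randomized count, so a perforation, dissection, vascular complication or major bleed caused by that denervation would be charged to sham.

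The 6-month analysis is the last safety comparison of the randomized arms before controls are split by crossover status. An event misplaced in this way can only raise the control rate. The error therefore runs in one direction, towards a smaller excess of events with RDN. Safety is also the domain in which a crossover procedure can itself generate endpoint events, yet it is the section without the limit.

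**Working it through.** The SAP gives no power, alpha or expected rate for the secondary safety comparison, so there is no planned figure to reproduce. The check is day arithmetic, followed by an illustration of size.

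**1. Overlap**

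- Lower edge of the 6-month window: day 166 (9.9.2, given as an example for the denominator).
- End of the count: day 180 (9.9.2).
- Overlap for an in-window visit: 180 − 166 = 14 days at most.
- For a control seen on day 166, the 30 days allowed by 9.1.4 run to day 166 + 30 = 196. So 14 of those 30 days (47%) lie inside the 6-month count.
- Nothing in 9.1.4 or section 7 makes crossover wait until day 180.

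**2. Number of controls**

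Section 8 randomizes subjects 1 to 106 at 1:1 and later subjects at 2:1, with a maximum of 260. It is not clear whether 260 includes the first 80.

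| Reading | Controls |
|---|---|
| 260 is the prospective cohort | 26/2 + (260 − 26)/3 = 13 + 78 = 91 |
| 260 is the whole study | 53 + (260 − 106)/3 ≈ 104 |
| Prospective 260 plus the 40 prior controls | 91 + 40 = 131 |

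All three are ceilings on the number at risk. Section 9.1.4 provides for subjects who were already past their 6-month visit when crossover became available, and those controls could mostly not have been denervated by day 180.

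**3. Expected misplaced events**

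Formula: controls × share crossing over by day 180 × event rate.

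- Share: not in the SAP. Assumed 5 to 20%.
- Event rate: 3.5%, the planning MAE rate in 9.9.1.1. As a check on that source, the exact binomial with n = 253 and at most 11 events gives one-sided alpha 0.0496, power 82.0% and an upper bound of 7.09%, in line with the SAP's 80% and 7.09%. The rate is used as an upper guide only. It covers one month (six for stenosis) and includes deaths and hypertensive-crisis admissions, whereas the overlap is at most 14 days.

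| Controls | 5% cross over | 10% | 20% |
|---|---|---|---|
| 91 | 91 × 0.05 × 0.035 = 0.16 | 0.32 | 0.64 |
| 104 | 0.18 | 0.37 | 0.73 |
| 131 | 0.23 | 0.46 | 131 × 0.20 × 0.035 = 0.92 |

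Addition to the control rate: 0.05 × 3.5% = 0.175 percentage points, up to 0.20 × 3.5% = 0.70 percentage points, whatever the number of controls.

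Chance of at least one such event, 1 − 0.965^(number crossing over): with 91 controls and 5%, 1 − 0.965^4.55 = 15%; with 131 controls and 20%, 1 − 0.965^26.2 = 61%.

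**4. Can one event matter?**

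In a hypothetical table chosen to lie near 0.05, RDN 7/209 against control 0/131 gives a Fisher p of 0.046; with one event added to control (1/131) it is 0.159. This shows only that the test is sensitive when counts are low. It is not a forecast.

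**The case against.** The strongest reply is that the SAP plainly intends to separate the two periods. Section 9.9.2 compares the arms to 6-month follow-up, says that crossover comes after it, and then reports Crossovers as their own group. Section 9.1.4 gives crossovers their own post-procedure schedule, and 9.9.7 and 9.9.8 spell out the limit. This is fair as evidence of intent, and the omission looks unintended. It does not settle the matter, because the separation follows the visit while the numerator follows day 180. Programmed as written, the count would keep the event in the control arm.

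Several stronger readings are tempting, and the SAP does not support them:

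- **That controls are allowed to cross over from day 166.** The SAP never says so. Day 166 is an example of a last-contact threshold for the denominator. Reading it as the earliest crossover day is an inference from 9.9.2 and 9.1.4 together. Three things must coincide: an early visit, a procedure before day 180, and an adjudicated event by day 180. The protocol, which is not at hand, may govern crossover timing more closely.
- **That the event is counted on both sides of a comparison.** It is not. The two-arm test has no Crossover column and the three-group summary has no pooled control column. One event could appear in two separate tables under different labels.
- **That the control rate is inflated by a large relative amount.** Any such figure needs a baseline control rate, which the SAP does not give.
- **That the primary safety conclusion is at risk.** That test is a single-arm performance goal in denervated patients, with no control rate in it. Table 2 lists crossovers among its sources, so a crossover complication may count there as a denervation event, which is appropriate.

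**Conclusion.** The point stands as a minor one. Followed literally, the 9.9.2 algorithm could score a complication of a crossover denervation done before day 180 as a sham-control event, and this would bias the 6-month RDN versus control safety comparison in favour of RDN.

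The true size cannot be known from the SAP. Under the assumptions shown it is below one expected event (about 0.2 to 0.9), and it would be smaller if few controls cross over early or if procedural risk is below the planning rate.

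The reach is narrow: one unpowered secondary time point. The 1- and 3-month comparisons fall before any crossover can open, and the criterion for study success is untouched. What lifts this above a matter of wording is that a stated rule can give a wrong result in one direction only, and that it is inconsistent with 9.9.7 and 9.9.8.

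**What to change.** Add to the algorithm in 9.9.2:

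- For RDN versus control comparisons to 6 months, count control events only up to the earlier of the time of interest and the day before the crossover procedure.
- Report events on or after the crossover procedure under Crossovers.
- Keep in the control denominator any control who completed the 6-month visit before crossing over.

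This brings 9.9.2 into line with 9.9.7 and 9.9.8. The cost is a short addition to the SAP and one date condition in the program. Control follow-up is shortened by at most 14 days in the few in-window subjects who cross over before day 180.

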9.9.2. Secondary Safety Objectives

The following secondary safety endpoints will be assessed:

- Acute/Procedural Safety Secondary Endpoints – Compared Between Groups at 1 Month Post-Procedure
 - Significant embolic event resulting in end-organ damage
 - Renal artery perforation requiring intervention
 - Renal artery dissection requiring intervention
 - Vascular complications
 - End-stage renal disease (ESRD)
 - $\geq 40\%$ decline in eGFR
 - Increase in serum creatinine $>50\%$ from screening visit 2
 - New myocardial infarction
 - New stroke
 - Renal artery re-intervention
 - Major bleeding according to TIMI definition (i.e. intracranial hemorrhage, $\geq 5\text{g/dl}$ decrease in hemoglobin concentration, a $\geq 15\%$ absolute decrease in hematocrit, or death due to bleeding within 7 days of the procedure)
 - New renal artery stenosis $>70\%$
 - Hospitalization for hypertensive crisis not related to confirmed non-adherence with medication and/or protocol
- Chronic Safety Secondary Endpoints - Compared Between Groups at 3, 6, 12, 24, and 36 months post-randomization.
 - Composite Safety Endpoint, defined as a composite of the following events:
 - All-cause mortality
 - End-stage renal disease (ESRD)
 - Significant embolic event resulting in end-organ damage
 - Renal artery perforation requiring intervention
 - Renal artery dissection requiring intervention
 - Vascular complications
 - Hospitalization for hypertensive crisis not related to confirmed non-adherence with medications and/or the protocol
 - New renal artery stenosis $>70\%$

- $\geq 40\%$ decline in eGFR
- Increase in serum creatinine $>50\%$ from screening visit 2
- New myocardial infarction
- New stroke
- Renal artery re-intervention
- Major bleeding according to TIMI definition (i.e. intracranial hemorrhage, $\geq 5\text{g/dl}$ decrease in hemoglobin concentration, a $\geq 15\%$ absolute decrease in hematocrit, or death due to bleeding within 7 days of the procedure)
- Hospitalization for hypertensive crisis not related to confirmed non-adherence with medication and/or protocol
- Summary of Health-related Quality of Life (HRQoL) analysis based on reporting measures using accepted QoL instruments (EQ5D)

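### SAP 9.9.2 tests RDN vs Crossover vs Non-Crossover on safety to 36 months, but crossover status is set after randomization by facts that overlap the endpoints, so the test is not a treatment comparison.

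*SAP*

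**What the plan says.** Up to 6 months, SAP 9.9.2 compares RDN with control using Fisher's exact test. After that it divides the control arm: "RDN vs. Crossover vs. Non-Crossover groups will be compared out to 36 months post-procedure using chi-square tests for categorical data", with ANOVA for continuous data. The same section closes with "The secondary safety analyses will be performed using the ITT population defined in section 9.1.3.1", and 9.1.3.1 defines that population by randomized treatment.

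Section 9.1.4 decides who is a Crossover:
- "Control subjects may crossover to receive renal denervation therapy after completing their 6 month follow-up visit".
- "To crossover, the required baseline data must be collected, and the subject cannot meet any of the anatomical or eGFR exclusion criteria".
- A control may decline, and the offer is made once.
- For those already past 6 months when crossover became available, "the decision to crossover must take place at their next in-person visit (6, 12, 24 and 36-month follow-up or Unscheduled visit"), so crossover can come well after month 6.
- "Subjects who do not meet required eligibility for crossover on the day of the procedure" go back to their original follow-up schedule.

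The chronic endpoints in 9.9.2 include all-cause death, ESRD, an eGFR decline of at least 40%, a creatinine rise above 50% and new renal artery stenosis above 70%. Under the rate algorithm in that section, anyone with an adjudicated event before the time point stays in both numerator and denominator.

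The time origin varies. The list in 9.9.2 has the chronic endpoints "Compared Between Groups at 3, 6, 12, 24, and 36 months post-randomization". Section 5.2 and the comparison text in 9.9.2 count from the procedure.

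**The concern.** Group membership is fixed after randomization by survival, renal function, renal anatomy and choice. The first three overlap with the outcomes being compared. A control who dies in month 4, or whose eGFR or anatomy rules out crossover, can only be a Non-Crossover, and the event is then carried to every later time point. A Crossover must have been alive and eligible up to the crossover procedure. The RDN arm passes through no such filter. This is immortal-time and selection bias built into the grouping.

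Long-term renal safety is a stated secondary objective. A significant three-group test could appear with no device effect at all, and a real difference between the randomized arms could be obscured. For a crossover, the two time origins differ by at least 6 months. The SAP does not say in which group that subject's pre-crossover events are counted.

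**Working it through.** The SAP gives no event rate, crossover fraction or power for this comparison, so there is no figure of its own to reproduce. The check asks what the grouping does when the arms do not differ.

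**Assumed inputs (none is in the SAP)**
- E36: 36-month event risk, the same in every arm, constant hazard; 5%, 10% or 20%.
- E: risk up to the crossover time t months, E = 1 − (1 − E36)^(t/36).
- q: share of pre-crossover events that bar crossover; 0.5 to 1.
- c: share of eligible controls who cross over; 0.3 to 0.8.

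**Formulas**
- RDN rate = E36.
- Non-Crossover rate = [qE + (1 − c)(E36 − qE)] / [qE + (1 − c)(1 − qE)].
- Crossover rate, timed from randomization = (E36 − qE)/(1 − qE). Timed afresh from the crossover procedure, it is E36.

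**E36 = 10%, crossover at 6 months**

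E = 1 − 0.9^(1/6) = 0.0174.
- Lower end (c = 0.3, q = 0.5, qE = 0.0087): (0.0087 + 0.7 × 0.0913)/(0.0087 + 0.7 × 0.9913) = 0.0726/0.7026 = 10.3%.
- Upper end (c = 0.8, q = 1): (0.0174 + 0.2 × 0.0826)/(0.0174 + 0.2 × 0.9826) = 0.0339/0.2139 = 15.9%.
- Crossover from randomization: 0.0826/0.9826 = 8.4% (q = 1) to 0.0913/0.9913 = 9.2% (q = 0.5).

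| E36 (= RDN rate) | Non-Crossover, crossover at 6 months |
|---|---|
| 5% | 5.2% to 8.1% |
| 10% | 10.3% to 15.9% |
| 20% | 20.6% to 30.2% |

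**Late crossover.** With E36 = 10%, c = 0.8, q = 1 and every crossover at 12 or 24 months, Non-Crossover shows 20.9% or 29.2%.

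**Three-group test under no difference.** I took 260 prospective subjects in addition to the first 80 (an assumption). RDN = 40 + 13 + 156 = 209 and control = 40 + 13 + 78 = 131. With E36 of 10% or 20%, c of 0.5 or 0.8, crossover at 6 months and the same risk for every subject, the simulated rejection rate of the nominal 5% chi-square test is about 5% to 29%.

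**Choice.** Let risk vary between subjects and be linked to choice, with an E36 parameter of 10%, c = 0.5, q = 0.5 and the clock restarted at crossover.
- Lower-risk controls tend to cross over: RDN 9.3%, Crossover 6.0%, Non-Crossover 13.0%.
- Higher-risk controls tend to cross over: RDN 9.3%, Crossover 12.3%, Non-Crossover 7.2%.

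The sign reverses between the two. Across the settings run, the rejection rate reached about 72% when lower-risk subjects chose crossover.

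**Check of the remedy.** Pool the two control groups from randomization at E36 = 10%, c = 0.8, q = 1. Crossovers are 0.8 × 0.9826 = 78.6% of controls, at 8.4%. Non-Crossovers are 21.4%, at 15.9%. The weighted mean is 0.786 × 8.4% + 0.214 × 15.9% = 10.0%, equal to RDN.

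**Censoring at crossover does not give this.** Suppose 10% of subjects are ineligible with three times the hazard of the rest, and 80% of eligible controls cross over. Relative hazard in RDN is 0.1 × 3 + 0.9 × 1 = 1.2. In the controls left behind it is (0.1 × 3 + 0.18 × 1)/0.28 = 1.71. That is a spurious ratio of 1.71/1.2 = 1.43.

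**The case against.** There are several fair points on the plan's side.

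- **Scope.** The randomized comparison is kept to 6 months, trial success rests only on the two primary endpoints (5.1, 9.9), and 12-month stenosis has its own descriptive section (9.9.2.1). This stands, and it limits the point to secondary safety testing after 6 months.
- **ITT.** RDN stays as randomized and both control groups come from the control arm, so nobody changes arm. The ITT sentence can be read as saying only who is included. That is a fair reading. Even so, dividing one arm by a post-randomization fact is not an as-randomized comparison, and none is stated after 6 months.
- **Direction.** A reader might infer that the split makes RDN look safer overall. The documents do not support that. The eligibility rule favours RDN only against Non-Crossovers. Against Crossovers, RDN looks equal or worse. The three-group chi-square has no direction, and voluntary choice can reverse the sign.
- **Endpoints.** A reader might extend the argument to MI and stroke. Section 9.1.4 bars crossover on anatomical and eGFR grounds, so a non-fatal MI or stroke does not force Non-Crossover status. Whether a 40% eGFR decline does so depends on exclusion thresholds that the SAP does not give.
- **Size.** For pre-crossover events that always disqualify, the Non-Crossover rate is multiplied by about 1/(1 − c), which is 1.4 at c = 0.3 and 3.3 at c = 0.7. A reader might take that as the bias in the planned comparison. It is not, because 9.9.2 counts all events to 36 months and later events dilute the ratio.

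**Conclusion.** The point holds as a defect of the post-6-month secondary safety comparison and should be corrected. The three-group test mixes any device effect with the rule and the choice that formed the groups, so its p-value has no treatment interpretation.

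For crossover at 6 months, the eligibility rule alone puts the Non-Crossover rate at roughly 1.03 times (10.3/10.0) to 1.6 times (15.9/10.0) the RDN rate under no true difference. The excess is small when few cross over and larger when crossover is late. These sizes rest on assumed values of E36, q, c and crossover timing. The net direction is not established, because the SAP says nothing about who chooses crossover.

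The inconsistent time origin, the unstated place of pre-crossover events and the missing as-randomized comparison after 6 months rest on the text alone.

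**What to change.** In SAP 9.9.2:

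1. Make RDN against all controls as randomized, timed from randomization, the stated safety comparison to 36 months. Note that it is diluted because some controls receive the device.
2. Show RDN, Crossover and Non-Crossover descriptively, labelled non-randomized, with no hypothesis tests. Report crossovers' post-procedure events from the crossover procedure and count their pre-crossover events as control.
3. Use one time origin for the between-group comparison in 5.2 and throughout 9.9.2.
4. If an analysis censoring controls at crossover is wanted, add it as supportive only, stating that the censoring is informative because eligible controls leave and ineligible ones stay.

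The cost is SAP wording and table shells, with no new data. The price is a diluted long-term contrast and the loss of the three-group p-values.

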9.2. General Methodology

Descriptive statistics of continuous outcomes will be presented by treatment group and include sample size, mean, median, standard deviation, minimum and maximum. For categorical outcomes, the number and percentage of subjects in each category will be presented by treatment group. Statistical comparisons between treatment groups will be made using the independent samples t-test for continuous outcomes and Fisher's exact test for categorical outcomes. Paired t-tests will be used to compare changes in blood pressure from baseline to follow-up within each treatment group. All statistical analyses will be performed using SAS for Windows (version 9.2 or higher) or other widely accepted statistical or graphical software. Patient data listings and tabular and graphical presentations of results will be provided. Unless otherwise specified, a two-sided 0.05 level of significance will be used to declare treatment groups significantly different.

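### The safety-rate rule drops event-free subjects who are lost but keeps every subject with an event, which biases cumulative rates upward under non-informative loss; after 6 months, sparse three-group tables get a chi-square test with no small-count fallback

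*SAP*

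**What the plan says.** All of the main text is in SAP section 9.9.2.

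- **Denominator, subjects with an event:** "The denominator will include all subjects who either had a CEC adjudicated event prior to the time of interest". No minimum follow-up is asked of them.
- **Denominator, event-free subjects:** "or had last contact date that is beyond the lower window of the follow up (166 days for 6 month events, for example". Those last seen earlier are left out.
- **Numerator:** "The numerator will include all subjects who had CEC adjudicated events up to the time of interest".
- **Time points:** "Chronic Safety Secondary Endpoints - Compared Between Groups at 3, 6, 12, 24, and 36 months post-randomization". The rule is written for the safety event rates in general; 6 months (180 and 166 days) is only its worked example.
- **Test to 6 months:** "The secondary safety endpoints, out to 6-months follow-up, will be compared between RDN and control groups using" Fisher's exact test.
- **Test after 6 months:** the three groups RDN, Crossover and Non-Crossover are formed, and these "groups will be compared out to 36 months post-procedure using chi-square tests for categorical data".

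The section names the ITT population and specifies no time-to-event method. Section 9.2 gives the general rule for two treatment groups, Fisher's "exact test for categorical outcomes", and adds that, unless otherwise specified, "a two-sided 0.05 level of significance will be used to declare treatment groups significantly different".

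**The concern.** Take two subjects who both leave at month 8. At the 12-month analysis, the one with an event is in the numerator and denominator, and the one without is in neither. The reported proportion therefore mixes event risk with retention. If retention differs between groups, equal risks can look unequal. That is plausible here: after unblinding at 6 months, control subjects choose whether to cross over (sections 7 and 9.1.4), so equal retention cannot be assumed.

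The test changes just as the tables become sparser. The control arm is split in two, and many listed components (ESRD, embolic event, perforation, dissection, stroke) may yield only a handful of events. At stake is whether the 12- to 36-month safety rates can be read as risks, and whether one isolated event could be reported as a significant group difference.

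**Working it through.** **1. Nearby SAP figures.** The SAP states no rate or operating characteristic for the post-6-month comparisons. Its exact-method figures reproduce: 2/50 gives 0.49% to 13.71% (stated 0.5%, 13.7%), and 11/253 = 4.3% has an upper bound of 7.09% (as stated).

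**2. Denominator rule.** Let R be the true cumulative risk at the visit and g the cumulative loss by then, with loss unrelated to events. R = 3.5% is the MAE rate assumed in section 9.9.1.1, used here as a reference value. g is an assumption.

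If events and loss both accrue steadily, about half the loss precedes a typical event:

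- events observed: E ≈ R(1 − g/2)
- event-free subjects retained: C = (1 − R)(1 − g)
- reported rate: E/(E + C)

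| g | E | C | Reported rate |
|---|---|---|---|
| 5% | 0.0341 | 0.9168 | 3.6% |
| 15% | 0.0324 | 0.8203 | 3.8% |
| 30% | 0.0298 | 0.6755 | 4.2% |
| 40% | 0.0280 | 0.5790 | 4.6% |

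Constant hazards to 36 months with a 14-day lower window give 3.6/3.8/4.2/4.5%. The same model at 6 months with 15% loss gives 3.7%, so the bias is not confined to later visits.

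If all events come before any loss, the reported rate is R/(R + (1 − R)(1 − g)):

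- g = 15%: 0.035/(0.035 + 0.965 × 0.85) = 4.1%
- g = 30%: 4.9%
- g = 40%: 5.7%

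On this early-event model, two groups with the same 3.5% risk and losses of 10% and 40% are reported as 3.9% and 5.7%.

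In a simulation of 400,000 subjects with 30% loss, a true 3.5% is reported as 4.2% by the SAP rule and 3.5% by Kaplan-Meier. A true 7.1% is reported as 8.5% and 7.2%.

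**3. Group sizes.** Section 8 gives 80 prior subjects at 1:1, then 26 at 1:1 and the rest at 2:1. Reading 260 as the prospective maximum leaves 260 − 26 = 234 at 2:1.

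- RDN: 40 + 13 + 156 = 209
- Control: 40 + 13 + 78 = 131
- Total: 340

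The crossover split of the 131 is not stated and is varied below. At 3.5% the expected count is 0.035 × 90 = 3.2 in a group of 90 and 0.035 × 41 = 1.4 in a group of 41.

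**4. One event in total, falling in the smallest group of size n out of N = 340.** The Pearson statistic is X² = [N/(N − 1)] × (N/n − 1). With 2 degrees of freedom, p = exp(−X²/2). The exact p is n/N.

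| Split | n | X² | Chi-square p | Exact p |
|---|---|---|---|---|
| 209/90/41 | 41 | 7.31 | 0.026 | 0.121 |
| 209/110/21 | 21 | 15.24 | 0.0005 | 0.062 |
| 209/66/65 | 65 | 4.24 | 0.120 | 0.191 |

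Chi-square passes 0.05 when X² > 5.99, which holds for n ≤ 48. The exact test needs n ≤ 17. A further case is events 1/0/2 in 209/90/41: chi-square p = 0.013, exact p = 0.083.

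**5. Average size of the chi-square test at nominal 0.05, by exact enumeration.**

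| Split | Rate 0.5% | Rate 1% | Rate 3.5% |
|---|---|---|---|
| 209/66/65 | 0.026 | 0.034 | 0.044 |
| 209/90/41 | 0.053 | 0.043 | 0.044 |
| 209/110/21 | 0.064 | 0.064 | 0.048 |

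Other group sizes widen the range at 0.5% to 1%: 169/46/45 (prospective subjects only) goes down to 0.020, and 226/85/49 (360 subjects, more than section 8 implies) goes up to 0.076.

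**The case against.** **Size of the inflation.** It rests on loss that the SAP does not state. The 15% attrition in section 8 concerns evaluable 6-month efficacy data, and missing an ABPM does not remove a subject from the safety denominator; only an early last contact does. At 5% to 15% steady loss, 3.5% becomes 3.6% to 3.8%. The direction assumes non-informative loss, and informative loss could reverse it. Upward bias in the treated arm works against the device. All of this stands, and limits the size of the point. The asymmetry itself remains.

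**Validity of the test.** A reader might infer that the chi-square p-values are wrong throughout, or that expected counts fall below 1 as a rule. Neither is supported. Average size is 0.044 to 0.048 at 3.5% in the 340-subject splits, and the error can go either way for rarer events. Counts below 1 need a very uneven split or rarer components. What remains is the unreliability of single p-values when events are few.

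**Conflict with section 9.2.** A reader might also see a contradiction there. Section 9.2 pairs Fisher's test with the independent-samples t-test for two treatment groups. Chi-square with ANOVA is the three-group counterpart, used the same way in sections 9.9.7 and 9.9.8. The gap is the missing small-count fallback, not an inconsistency.

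**Consequence.** Study success depends on the two primary hypotheses only (section 9.9), and primary safety is one exact binomial analysis of 253 subjects. That stands: no decision rule hangs on these comparisons.

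**Conclusion.** The point holds in two limited parts.

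First, the denominator rule biases cumulative safety rates upward at every visit when loss is unrelated to events, and more as loss accumulates. It is wrong to read this as a problem only after 6 months. Steady loss is assumed for the 3.6% to 4.6% range around a true 3.5%. With small loss the effect is negligible; with early events or unequal loss it is larger.

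Second, the post-6-month chi-square test has acceptable average size at 3.5% but is conservative or liberal for rarer events (about 0.02 to 0.08 at 0.5% to 1% over all splits tried). With few events its single p-values cannot be relied on: in 340 subjects, one event in a smallest group of 18 to 48 is significant by chi-square and not by the exact test. The crossover split is an assumption.

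The revision is worth making for the reporting of long-term safety. It does not put the primary safety conclusion in doubt through the choice of test.

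**What to change.** - **Rates.** For clinical events, report Kaplan-Meier estimates censored at last contact, with 95% confidence intervals and numbers at risk. For non-fatal components, use cumulative incidence with death as a competing event.
- **Comparisons.** Wherever proportions are compared across RDN, Crossover and Non-Crossover, replace chi-square with the Fisher-Freeman-Halton exact test. Label these comparisons descriptive, because the groups are self-selected after 6 months.
- **No log-rank test in its place.** It is also asymptotic with few events, and a corrected p-value would still not have a randomized interpretation.
- **Laboratory thresholds.** If the eGFR and creatinine endpoints stay as proportions, state the number of event-free subjects excluded from each denominator, by group and visit, since the asymmetry remains there.

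The cost is SAP wording and standard procedures, with no new data. The downside is that Kaplan-Meier and cumulative incidence rest on independent censoring, which should be stated.
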